#### Protocol deviations with respect to adherence

In other sensitivity analyses, we will also perform a per protocol analysis whereby we exclude participants, whose adherence to the grocery intervention was <85% based on

dietary compliance records. This will be reported in the Supplement of the primary paper.

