11. INTERVENTIONS

Distribution and adherence

Overview: Participants will be assigned to one of two 3-month interventions: (1) dietitian-assisted, DASH-patterned, home-delivered groceries ordered weekly through Amazon Fresh or Instacart over 12 weeks or (2) self-directed grocery shopping (monthly stipend and DASH eating plan brochure) over 3 months (referent). All participants will receive materials for addressing food insecurity, a set of measuring cups and spoons, a digital food thermometer, and page one of NHLBI's "Your Guide to Lowering Your Blood Pressure with DASH." 18,60

Self-Directed Shopping: These participants receive an unrestricted stipend of \$500/month (at 4, 8, and 12 weeks). There will be a call with the dietitian at week 8 to establish contact, check on the payments, and schedule FV1.

Dietitian-Assisted DASH Grocery Intervention: Participants randomized to the DASH grocery intervention will participate in weekly calls with the study dietitian. These calls will serve three purposes: (1) order groceries for the week, (2) assess compliance from the prior week's order, and (3) allow for education on fundamentals of healthy grocery shopping, meal storage, preparation, and in-home eating (**Table 3**).

Table 3: Curriculum
Module 1: Principles of DASH
Module 2: Food storage to reduce waste
Module 3: Sodium and potassium: What do they mean for your health?
Module 4: Quick food safety tips
Module 5: Enhance your favorite meal and explore something new
Module 6: Understanding nutrition labels
Module 7: Strategies to increase fruits and vegetables servings
Module 8: Quick and healthy meal prep
Module 9: DASH at Home
Module 10: DASH at restaurants and special events/holidays
Module 11: Smart Shopping
Module 12: Recap and DASH principles

Participants will also be provided instructions on how to receive food deliveries, food storage strategies to avoid spoiling, meal preparation tips, and example recipes that incorporate cultural foods and dishes. We will also prepare 24 instructional cooking videos (10-15-minute duration)

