We will ask participants assigned the DASH grocery intervention to list what foods they have left over from the previous week's order. This will allow the dietitian to quantify how much they consumed versus threw away from the previous week. They will also be asked to list consumption of non-protocol foods (e.g., dining out or grocery purchases beyond the study foods) and to characterize on a scale from 1 to 9, whether they liked the DASH eating plan. Finally, participants will be asked about the timeliness, accuracy, and quality (damage/spoilage) of food delivery throughout the intervention phase.

Two forms are designed to monitor adherence in the DASH grocery intervention group, the Knowledge Assessment Form (KNOW) and Diet Palatability (PAL) form. The KNOW will test the participants' knowledge on basic principles of the DASH Eating Plan before and after the study. The purpose is to assess the effectiveness of the education modules delivered by the dietitian.

Topics assessed are purposes of the DASH, role of sodium and potassium, compliant DASH foods, and high sources of sodium. PAL is meant to assess diet acceptability, implementation, and behavioral effects. Key information collected is how much non-study food they consumed during the intervention period (including reasons why), reasons why they did not finish all the study groceries, confidence entering the observation phase, likeliness to continue DASH when the study is over, and a general rating of the at-home grocery delivery service. This form also goes into significant detail about online grocery shopping. It assesses the likelihood of using an at-home grocery delivery service after the study is over, participant's confidence in ordering groceries online, and if they would recommend this program to family and friends. Lastly, this form gives the participants an opportunity to express their feelings about the intervention as a whole and provide suggestions they have for improvement.

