All GO calls will be scheduled at the randomization visit for the same time each week to encourage consistent adherence. If a participant does not pick up the first time, the study dietitian will leave a voicemail and call back in 5 minutes. If the participant still does not pick up, the dietitian will call back at the end of the business day and then attempt to reach the participant's emergency contact. At this point, a text message and email will be sent to the participant to give them the opportunity to ask for last week's order again if they are unable to talk on the phone that week. For those individuals without text or email access, groceries will not be sent to the house until the dietitian is able to get into contact with them. If over three weeks pass by with no contact, a letter will be sent to the participant's home to encourage reconnecting to the GoFresh team, as well as coming to the follow up visit.

Extension Period

An extension period is possible if a participant misses two weeks during the active 3-month intervention. The ultimate goal is for each participant to be active in the intervention for the two consecutive weeks preceding the follow-up visit. Because of this, there will be a greater emphasis on those who miss weeks 10-12. If a participant misses one visit between weeks 2-10; the dietitian will assess the best course of action. Options include doubling up on modules that are shorter in time, asking the participant if they can meet for a longer period of time during one of the visits, or combining similar modules. If a participant misses more than one visit between weeks 2-10, the GoFresh team will discuss and decide if an extension period is necessary. In general, a participant will only be extended for two weeks (weeks 13 or 14). Any other exceptions based on extenuating circumstances (e.g., COVID19, institutional requirements, etc.) will be discussed with the investigative team

If a participant states they do not want to receive groceries anymore, staff will still encourage them to come in for their follow up visit for a blood pressure measurement. If the participant states they wish to leave the study, the staff member will document this discussion and the staff will no longer reach out to this individual as delineated in their consent agreement.

12. Safety Safety Monitoring

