#### 3.2 Primary analysis

Our primary comparison is the net effect of randomized assignment (dietitian-assisted vs. self-directed shopping) on office SBP from baseline to 3- (primary) and 6-months post-randomization. Office SBP will be based on the average of three visits at baseline (two screening visits and the randomization visit each with 3 measurements; nine measurements total), two 3-month follow-up visits (each with 3 measurements; six measurements total), and two 6-month follow-up visits (each with 3 measurements; six measurements total). We will first confirm that the residuals of office SBP are normally distributed (if not it will be log-transformed). Modeling will be performed using generalized estimating equation (GEE) models with a treatment-by-visit interaction term. We will perform an intent-to-treat analysis. The visit term will be used to compare changes between 3 months versus baseline, 6 months versus 3 months, and 6 months versus baseline with a product (interaction) term to compare changes across intervention. Models will be adjusted for ZIP code or baseline blood pressure in sensitivity analyses.

Our hypothesis is that 12 weeks of dietitian-assisted, home-delivered, low sodium, DASH groceries will lower office SBP compared to 12-weeks of self-directed grocery shopping. The null hypothesis is that there will be no difference in office SBP between the two intervention arms. The comparison between the two treatment groups will be performed by comparing the regression coefficient for treatment with zero (a two-sided alpha of <0.05 will be considered statistically significant for the primary comparison at 3-months.

For additional pre-specified sensitivity analyses and subgroups to assess effect medication, see below.

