## 4 Other outcomes

#### 4.1 Adherence

Compliance will be quantified by (1) 24-hour urine sodium and potassium (2) 24-hr dietary recall, estimating servings of DASH food groups as well as nutrients consumed, (3) Rapid Block screener for fruit, vegetable, fat, and sodium, and (4) DASH Diet Index. The data will be reported by treatment group.

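### Does the SAP's per-protocol analysis, whose 85% grocery-adherence rule can filter only the DASH arm, need to be changed?

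*SAP*

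**What the plan says.** SAP 3.4 Sensitivity analyses, under the heading on adherence deviations, introduces the analysis with "In other sensitivity analyses, we will also perform a per protocol analysis". The rule is to "exclude participants, whose adherence to the grocery intervention was <85% based on" a named source: "dietary compliance records. This will be reported in the Supplement of the primary paper". The SAP gives no formula for the percentage.

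The Protocol, section 11, shows where such records come from. Under Monitoring Adherence: "We will ask participants assigned the DASH grocery intervention to list what foods they have left over" from the week before, so that the dietitian can work out how much was eaten and how much thrown away. Foods from outside the study are listed as well. Section 7 adds a weekly food-use worksheet completed at the grocery ordering calls. The self-directed arm has one dietitian contact in the same period: "There will be a call with the dietitian at week 8 to establish contact, check on the payments, and schedule FV1".

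Section 11 also allows catch-up weeks: "An extension period is possible if a participant misses two weeks during the active 3-month intervention".

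SAP 4.1 describes compliance measures reported for both arms: "Compliance will be quantified by (1) 24-hour urine sodium and potassium (2) 24-hr dietary recall", followed by a food screener and a DASH index. None carries an 85% cut-off. For the primary comparison, SAP 3.2 states: "We will perform an intent-to-treat analysis".

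**The concern.** Controls have no study groceries, so they cannot fall below 85% on adherence to them. The rule removes people from one randomised arm because of what they did after randomisation and leaves the other arm whole. If those who keep to the groceries would have had a more favourable SBP course anyway, the filtered comparison shows a benefit that the groceries did not cause. The SAP has no matching control exclusion, no adjustment and no caveat.

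The 85% also has no written numerator, denominator or period, and nothing on extension weeks, shared food or missing records. Who is excluded depends on choices that could in principle be made after the data are seen.

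At stake is the reading of a Supplement table: a larger per-protocol effect taken as the effect when the plan is followed, or agreement with the main result taken as evidence of robustness.

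**Working it through.** **1. Does the rule reach only one arm?** Set side by side, SAP 3.4 scores adherence to the grocery intervention, and Protocol 7 and 11 collect grocery-use records from DASH participants only. Controls receive a stipend, a brochure and the week-8 call. As worded, yes.

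**2. Design figures, for scale.** SAP 3.3 gives 75 per arm, SDs 11.85 and 11.4, difference 5.8 mm Hg, power 0.85, two-sided 0.05.

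- Pooled SD = sqrt((11.85² + 11.4²)/2) = 11.63.
- Standard error = 11.63 × sqrt(2/75) = 1.90.
- Power = Φ(5.8/1.90 - 1.96) = 0.86, in line with the stated 0.85.

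The 85% adherence cut-off is a bare threshold with nothing to reproduce.

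**3. How large could the selection effect be?** Assume no true effect and exclude the least adherent share q of the DASH arm. Let r be the correlation between adherence and lower SBP that the groceries do not cause. Then

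false difference = -r × SD × φ(z_q)/(1 - q).

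The SD is 11.4 (SAP 3.3). Both r and q are assumptions, because the documents give neither. Example: q = 0.20, r = 0.1 gives φ(z_q)/(1 - q) = 0.350, and -0.1 × 11.4 × 0.350 = -0.40 mm Hg. Rejection rates at the two-sided 5% level come from 6,000 simulated trials per cell, starting from 75 per arm.

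| Share excluded | r = 0 | r = 0.1 | r = 0.2 | r = 0.3 |
|---|---|---|---|---|
| 10% | 0 (5.1%) | -0.22 (5.7%) | -0.44 (5.6%) | -0.67 (6.5%) |
| 20% | 0 (5.6%) | -0.40 (5.6%) | -0.80 (7.0%) | -1.20 (8.7%) |
| 30% | 0 (5.6%) | -0.57 (5.8%) | -1.13 (8.4%) | -1.70 (13.0%) |
| 40% | 0 (5.1%) | -0.73 (6.4%) | -1.47 (10.5%) | -2.20 (18.2%) |

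The largest entry is 2.20/5.8 = 38% of the design difference. A negative r gives the same sizes with the sign reversed. In a separate run of 20,000 trials with an assumed SD of change of 10.5, the intent-to-treat test stayed at 4.9% to 5.3% throughout.

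**4. Does the definition of 85% matter?** It can. If weekly orders were counted, someone who missed two weeks and was extended to week 14 would score 10/12 = 83%, 12/14 = 86% or 12/12 = 100%. But the Protocol's records concern food consumed out of what was ordered, not a count of orders. In an illustration with assumed mean consumption of 90%, and 0, 1, 2 or 3 missed weeks in 60%, 20%, 10% and 10% of participants, about 20% are excluded on consumed/delivered, 20% on orders/12 and 44% on their product.

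**5. Would an instrumental-variable estimate do better?** Take the randomised arm as instrument and the share of groceries consumed as exposure, with controls set to 0. Without covariates the estimate is

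intent-to-treat difference / mean DASH adherence.

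For assumed mean adherence of 0.91, 0.86 and 0.81 and an intent-to-treat difference of -5.8:

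- -5.8/0.91 = -6.4
- -5.8/0.86 = -6.7
- -5.8/0.81 = -7.2

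The standard error scales in the same way: 1.5/0.91 = 1.6 and 1.5/0.81 = 1.9, against simulated values of 1.7 to 1.9. In 3,000 simulated trials per scenario, its significance agreed with intent-to-treat in at least 99.5%. If the effect does not in fact depend on how much of the groceries is eaten, the mildest scenario overstates it by 6.4 - 5.8 = 0.6 mm Hg. That exceeds the 0.40 mm Hg selection effect at r = 0.1 with 20% excluded.

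**The case for a change.** The strongest case for a change is that the facts are right and the remedy is cheap. One arm is filtered, the SAP does not say so, and the term per protocol does not by itself tell a reader that controls were left untouched. A definition carries most weight when fixed before outcomes are seen by arm. Defining the percentage and adding a sentence on interpretation would need no new data, and the upper end of the table is a sizeable part of 5.8 mm Hg.

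The description stands: as worded, the rule is one-sided, and the denominator, the period and the handling of extension weeks and missing records are not written down. The consequence does not follow. One-sided filtering is inherent in a per-protocol set when controls receive no study product, and a trial readership knows that such a set is selected after randomisation. The cut-off and the type of record are fixed in advance, and Protocol 10 keeps investigators masked until data collection ends. That reduces, without removing, the room for a convenient definition. A sentence calling the comparison non-randomised would help the reader but would alter no estimate, and omitting the P value is a matter of taste.

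The instrumental-variable model would be correct if the effect were proportional to groceries eaten. It assumes that assignment acts only through the groceries, and the weekly teaching and the control stipend, both part of the design, may breach that. It also needs the same consumption score that is said to be undefined.

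**Conclusion.** No change to the plan follows. The analysis does compare selected DASH participants with all controls, and it can mislead by up to about 2 mm Hg over the range examined (r from 0.1 to 0.3, 10% to 40% excluded). That range is assumed: the documents fix neither the size nor the direction of the bias, and it is zero if adherence is unrelated to SBP apart from the groceries. The trial's conclusion rests on the 3-month intent-to-treat comparison, which this rule does not touch.

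The missing formula is detail that analysts can fill sensibly: food consumed relative to food ordered, taken from the weekly records, with extension weeks and missing records settled before unmasking and the number excluded shown beside the result. An instrumental-variable analysis would add no independent check, only a rescaled intent-to-treat estimate and an assumption open to doubt in this design.

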## 4 Other outcomes

#### 4.1 Adherence

Compliance will be quantified by (1) 24-hour urine sodium and potassium (2) 24-hr dietary recall, estimating servings of DASH food groups as well as nutrients consumed, (3) Rapid Block screener for fruit, vegetable, fat, and sodium, and (4) DASH Diet Index. The data will be reported by treatment group.

#### 4.2 Secondary Endpoints

We will examine the effect of the DASH-patterned grocery intervention on the following additional outcomes, testing the null hypothesis that there is no difference in the following outcomes between the DASH-patterned groceries and the self-directed intervention. We will examine the distribution of all variables. We will use generalized estimating equations with a robust variance estimator and a normal family identity link for normally distributed outcomes or a binomial distribution, logit link for binary outcomes. A visit term will be used to compare changes between 3 months versus baseline, 6 months versus 3 months, and 6 months versus baseline with a product (interaction) term to compare changes across intervention. Continuous variables with non-normal residuals will be log-transformed with effects reported as a percent change. If residuals are still not normally distributed even after log transformation, we will apply non-parametric approaches.

- Seated, office-based, diastolic blood pressure: This will be based on the average of three visits at baseline (two screening visits and the randomization visit each with 3 measurements; nine measurements total), two 3-month follow-up visits (each with 3 measurements; six measurements total), and two 6-month follow-up visits (each with 3 measurements; six measurements total). This is a continuous variable that we anticipate will follow a normal distribution.
- Ambulatory blood pressure monitoring: We will determine the mean waketime systolic and diastolic blood pressure (intervention & observation phases) measured at baseline, 3-months, and 6-months after randomization. This is a continuous variable that we anticipate will follow a normal distribution.
- Body Mass Index (BMI): This is derived from a height measurement at baseline and two weight measurements at baseline, 3-months, and 6-months. This is a

continuous variable that we anticipate will follow a normal distribution.

- 24-hour urine potassium/creatinine and sodium/creatinine ratio: This is collected after a clinic void over a 24-hour period at baseline, 3-months, and 6-months. These continuous variables are often skewed and may require log-transformation in which case they will be reported as a percent change. We will examine potassium/24hr period and sodium/24hr period as well.
- Hemoglobin A1c: Measured in whole blood at baseline, 3-months, and 6months. This is a continuous variable we anticipate will follow a normal distribution.
- Lipid concentrations: Measured in fasted serum specimens collected at baseline, 3-months, and 6-months. This includes total cholesterol, high density lipoprotein cholesterol, derived low density lipoprotein cholesterol, and triglycerides. These are continuous variables. Triglycerides typically require log-transformation. We will examine the distributions of the other lipid types prior to analysis.
- Serum potassium and creatinine: Measured in fasted serum at baseline, 3months, and 6-months as part of a basic metabolic panel. These are continuous variables we anticipate will follow a normal distribution.
- **Daily intake of fat, fruits, and vegetables:** Assessed via questionnaire inperson and via phone call using a validated food screener. This is a measure of adherence. We will focus on assessments performed at baseline, 3 months, and 6 months after randomization (12-month assessments will not be the focus of our primary analysis). We anticipate this continuous variable may have a non-normal distribution, requiring log-transformation.
- 24-hour dietary recall: Assessed via questionnaire measured at baseline, 3months, and 6-months after randomization. This will be used to determine a DASH Diet Index. We anticipate this will not follow a normal distribution, requiring log-transformation.

## 5 Missing data

We will employ a number of recommended strategies to prevent missing data:

- A simplified data collection schedule that minimizes participant burden;
- Intention-to-treat analysis that includes following participants according to the data collection schedule regardless of compliance with the study intervention;
- Frequent engagement with the participants through visit reminder calls or notes;
- Contiguous windows of time during which specific follow-up visits are allowed;
- Monetary incentives to encourage enrollment and continued participation;
- Rigorous training of clinic staff emphasizing the importance of
  - Positive and warm interpersonal relationships between the participants and study staff
  - Study commitment during the consent process to ensure that potential participants understand the importance of completing the study
  - $\circ$   $\,$  Addressing participant concerns to minimize dissatisfaction  $\,$
  - $\circ$   $\,$  Collecting data even if a participant discontinues the study treatment
  - Reasons for any drop-outs will be documented.

We will perform the following sensitivity analyses using established methods for addressing missingness in clinical trials: use of out-of-window blood pressure measurements, multiple imputations at the individual level, and best and worst-case scenarios. We will compare the results from these approaches with primary analysis results to assess the primary result's robustness to the effects of missing data. Further, we will compare the baseline characteristics of complete cases and participants with missing measures between the two assignments.

### 6 Safety outcomes

We will compare self-reported symptoms that are thought to potentially arise from the diet. The symptoms will be summarized by the counts and proportions of participants in each group and overall. The treatment groups will be compared with respect to safety outcomes by using a chi-square test (Fisher exact test when there are cell counts less than 5).

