- **Screening Visits (SVa & SVb)** A series of 2 in-person visits performed at the CRC or Bowdoin Street Health Center to determine eligibility, describe the trial plan, and obtain written informed consent (SVa). Participants will be screened for health-related social needs including food insecurity modified to reflect the last 3 months. Participants will be asked for demographic information, an expanded medical history, contact information, health communities questionnaire, baseline fruit and vegetable consumption,9 and estimated resting metabolic rate (Mifflin St Jeor/International physical activity questionnaire).³⁷ We also will administer the SHoPPER questionnaire on shopping habits, food preparation, and dining behaviors. 38,39 Participants also will be asked to rate the baseline presence of symptoms related to the DASH eating plan (e.g. bloating, etc.) adapted from the DASH-Sodium trial. 12 Participants will subsequently undergo physical measures (height, weight, office BP), phlebotomy, and will return home with equipment for 26-hour BP monitoring and 24-hour urine collection (dropped off at the CRC 1-2 days later; during the SVb visit). SVb will also include questionnaires to assess perceived health, stress, and discrimination. SVb will also include a 24-hour recall that coincides with the 24-hour urine timeline. To facilitate high through-put and accessible screening, SVa may be split into a "mini" visit focused on the demographic and contact information, the food insecurity screening instrument, and the first set of blood pressure measurements. Eligible participants at the "mini" are invited back to complete the remaining components of SVa.

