- 3. Food shopping, meal preparation, and dining behaviors and habits will be assessed via the interviewer-administered SHoPPER questionnaire^{38,39} at the (SVa, RZ, FV1a, FV2a, FV3), which has been adapted for this study. A 24-hour recall will also be conducted by a certified study staff member at visits SVb, FV1b, and FV2b, using the Automated Self-Administered 24-Hour (ASA24®) Dietary Assessment Tool.
- 1. Other Measures (Questionnaires): The Accountable Health Communities Health Related Social Needs Screening Tool⁴¹ will be interviewer-administered at SVa to examine the prevalence of health-related social needs among participants at baseline. The Perceived

Stress Scale⁴¹ will be administered at SVb, FV1b, FV2b, FV3 to assess the participant's feelings on stress. In addition, all participants will complete the 2-item Hunger Vital Sign, ^{49,50} a food insecurity screener, at SVa, FV1a, FV2a, and FV3. The IPAQ⁵¹ will be used at SVa and RZ with the Mifflin-St. Jeor estimator (along with age, sex, and BMI) to estimate resting metabolic rate (average across visits) to determine the amount of groceries. A Diet Symptoms Questionnaire adapted from the DASH-Sodium trial will be administered at SVa, FV1a, FV2a, and FV3 to document any dietary reactions, including light-headedness, bloating, headaches, or fatigue. Medication lists will be assessed via pill bottle evaluation at SVa and updated throughout the study (RZ, FV1a, FV2a, and FV3). We will closely monitor for the addition of anti-HTN medications between visits. Grocery order sheets from the intervention phase will be used to compare the micronutrient profile of the intervention, using ESHA software (Salem, OR) and for exploratory stratified analyses based on the distribution of specific food items or micronutrients (e.g., potassium).

RE-AIM Secondary Endpoints: Reach & Implementation (Specific Aim 3)

- 1. Reach: We will track referrals, participation rates, and recruitment yields as in prior work. 52,53
- Implementation: The SF-12 will assess global health-related quality of life at SVb, FV1b, FV2b, and FV3. A standard intervention costing instrument will gather costs of groceries and dietitian salary and effort gathered over study phases through structured interviews of staff, financial records, and direct observation. Beyond these instruments we will also track process information (e.g., Run-in Visit results), that can be used to access scalability.

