- For an average SBP of 160-179 mm Hg or DBP of 105-109 mm Hg, we will recommend that the participant seek care with usual provider within 1 month and email the study clinical team
- For an average SBP ≥ 180 mm Hg or DBP ≥ 110 mm Hg, we will recommend that the participant seek same day care with usual provider, urgent care or a local emergency room and page/call the study clinical team

Identifying patients with low blood pressure (hypotension)

We anticipate that the intervention will decrease participants' BP. If we discover an unusually low blood pressure at our study visits, we will implement safety procedures as follows:

• For an average SBP < 90 mm Hg or DBP < 50 mm Hg with symptoms (described below), we will recommend the participant seek same day care with usual provider, urgent care or a local emergency room and page/call the study clinical team.

If participants have NEW or SEVERE symptoms such as nausea, vomiting, shortness of breath, chest pain, headache, vision changes, lightheaded or dizziness, fainting, or loss of consciousness during blood pressure assessment, they will be referred for same day care with their usual care provider, urgent care or a local emergency room regardless of blood pressure level.

Identifying patients with lab abnormalities

As part of this study, we may discover lab values that are outside of the normal range. All lab results will be reviewed by the study team within 72 hours. Participants will be notified of lab results and given recommendations for follow-up care with their usual care provider.

The intervention will provide groceries that are higher in potassium than a typical American diet. In general, in healthy individuals, a DASH-style diet should not increase potassium levels outside the normal range. Nevertheless, we may incidentally discover abnormal potassium levels during this study.

Hyperkalemia is defined as a serum potassium ≥ 5.5 mEq/L. If hyperkalemia is detected in the absence of hemolysis, investigators will do the following:

- For mild hyperkalemia with hemolysis (K = 5.5-6.4), we will recommend repeating the lab within 48-72 hours and contact the study clinician team
- For mild hyperkalemia without hemolysis (K = 5.5-6.4), we will recommend repeating the lab same day and page/call the study clinician team
- For severe hyperkalemia (K > 6.4), we will recommend repeating the lab same day and page/call the study clinician team.

Adverse event surveillance and reporting procedures

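### The SAP's symptom comparison uses no baseline adjustment and names no visit, which gives up precision, and protocol-defined safety events get no table by arm

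*SAP*

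**What the plan says.** SAP section 6 is short. Its subject is symptoms only: "We will compare self-reported symptoms that are thought to potentially arise from the diet". The summary is by participant: "The symptoms will be summarized by the counts and proportions of participants in each group and overall". The test is then given: "The treatment groups will be compared with respect to safety outcomes by using a chi-square test", with Fisher's exact test for cell counts below 5. It states no visit, no rule for when a symptom counts as present, and no role for baseline.

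Protocol section 7 shows that the baseline is available. At screening, "Participants also will be asked to rate the baseline presence of symptoms related to the DASH eating plan". The form is then repeated: it is "administered at SVa, FV1a, FV2a, and FV3 to document any dietary reactions, including light-headedness, bloating, headaches, or fatigue". That is one baseline and three follow-up administrations (3, 6 and 12 months).

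Protocol section 12 (Safety) sets event thresholds. "Hyperkalemia is defined as a serum potassium ≥ 5.5 mEq/L", and low blood pressure calls for action at an average SBP below 90 or DBP below 50 mm Hg with symptoms. Serious adverse events are defined there and reported individually to the IRB and onward to the DSMB. No section of the SAP tabulates any of these by arm.

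The SAP does compare related measures by arm. Sections 1.2 and 4.2 list serum potassium, creatinine and office DBP at 3 and 6 months, and section 3.2 covers office SBP. All are analysed by GEE with a visit-by-treatment term.

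**The concern.** Symptoms such as headache or fatigue can be present before any diet change. A participant who has a symptom at screening is more likely to report it again at 3 months whichever arm they are in. An unadjusted comparison treats that stable between-person variation as noise, although the trial has already measured it. Section 4.2 of the SAP uses baseline for every secondary outcome; section 6 does not, and gives no reason.

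The missing visit leaves a choice open until the data are in. Four named symptoms at three follow-up visits give 12 possible tests, before any decision about what rating counts as present.

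The missing event table is a reporting gap. The groceries are planned to be higher in potassium than a typical diet and the intervention is expected to lower blood pressure. A difference in means cannot tell a reader how many participants crossed the protocol's own thresholds.

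**Working it through.** **Inputs from the documents.** 75 analysed per arm, 1:1 allocation, two-sided 0.05, SDs 11.85 and 11.4, difference 5.8 mm Hg, power 0.85, 15% attrition, 176 randomised (SAP sections 3.1 to 3.3).

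**Inputs assumed.** The documents give no symptom prevalence, no baseline-to-follow-up correlation and no event rates. The ranges used are control prevalence 10-40%, effect 15-20 points and latent correlation 0.3-0.85.

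**Step 1: the plan's own figure.** Section 6 states none, so the only sizing to reproduce is the SBP power.
- Pooled SD = √((11.85² + 11.4²)/2) = 11.63; SE = 11.63 × √(2/75) = 1.90.
- Power = Φ(5.8/1.90 − 1.96) ≈ 0.86, against 0.85 stated.
- 150/0.85 = 176.5, against 176 stated.

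Both reproduce, so 75 per arm is a fair basis.

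**Step 2: what the planned test can detect.** With 80% power at 75 per arm, the unadjusted comparison of proportions detects 5% vs 20%, 10% vs 28%, 20% vs 41% or 30% vs 52%.

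**Step 3: effect of baseline adjustment, one case by hand.** Take 20% vs 35% with latent correlation 0.7.
- Unadjusted SE = √((0.20×0.80 + 0.35×0.65)/75) = 0.0719. Power = Φ(0.15/0.0719 − 1.96) = Φ(0.13) = 0.55.
- A latent correlation of 0.7 corresponds to a correlation φ of about 0.45 between the yes/no values at baseline and follow-up.
- Adjusted SE ≈ 0.0719 × √(1 − 0.45²) = 0.0642. Power = Φ(0.15/0.0642 − 1.96) = Φ(0.38) = 0.65.

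**Step 4: the range by simulation.** 4,000 trials per cell, 75 per arm; chi-square against a linear risk model with baseline symptom status and robust variance.

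| Control vs DASH | Latent correlation | Unadjusted | Adjusted | Gain (points) |
|---|---|---|---|---|
| 20% vs 35% | 0.3 | 0.53 | 0.56 | 2 |
| | 0.5 | 0.54 | 0.59 | 5 |
| | 0.7 | 0.56 | 0.65 | 9 |
| | 0.85 | 0.55 | 0.74 | 18 |
| 20% vs 40% | 0.3 | 0.77 | 0.79 | 2 |
| | 0.5 | 0.77 | 0.81 | 4 |
| | 0.7 | 0.78 | 0.87 | 9 |
| | 0.85 | 0.79 | 0.93 | 14 |
| 30% vs 50% | 0.3 | 0.72 | 0.72 | 1 |
| | 0.5 | 0.72 | 0.76 | 4 |
| | 0.7 | 0.72 | 0.81 | 9 |
| | 0.85 | 0.73 | 0.89 | 16 |

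Gains come from unrounded powers. A repeat with 6,000 trials per cell, extended to control prevalences of 10% and 40%, gave the same pattern, with extremes of about 0 and 20 points. With no true effect, rejection at 20% prevalence was 4.5-5.0% for both methods in the first run and 4.9% in the repeat. In the repeat it was 5.2-5.8% for both methods at 10% and 40%.

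**Step 5: what a by-arm event table can and cannot do.**
- Fisher's test needs 6 events vs 0 for p < 0.05 (p = 0.028 at 75 per arm, 0.029 at 88).
- Power for 1% vs 5% is 9% at 75 per arm and 14% at 88.
- Zero events in an arm leaves a two-sided 95% upper limit of 1 − 0.025^(1/n): 4.8% at n = 75 and 4.1% at n = 88.

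Tests are therefore close to uninformative; counts with intervals are not.

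**Step 6: can potassium events be counted as defined?** Protocol section 12 introduces its hyperkalemia actions as applying when hemolysis is absent, and then lists as its first action one for results with hemolysis. The two statements conflict, so whether a hemolyzed result counts as an event is undefined.

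**The case against.** The case for leaving section 6 alone is reasonable. The protocol calls the trial minimal risk. The diet risk it describes is mainly reactions to new foods and mild gastrointestinal discomfort, and a symptom comparison addresses that. It says a DASH-style diet should not in general push potassium out of range in healthy people, and entry excludes potassium of 5.0 or more and eGFR below 30. For descriptive safety data a simple test is defensible, and the gain from adjustment depends on correlations nobody has documented; at 0.3 it is negligible. Serious events are monitored through clinician review, the IRB and the DSMB.

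Most of this stands, and it rules out several stronger readings that a reader might infer:
- *That the safety conclusion rests on unmasked self-report alone.* It does not: potassium, creatinine and blood pressure are compared by arm elsewhere in the SAP. Nor would baseline adjustment remove reporting bias that arises after participants know their arm.
- *That the plan compares raw symptom counts.* Section 6 compares proportions of participants.
- *That the unadjusted test is biased or invalid.* Under randomisation it is neither.
- *That the analysis is weak wherever the protocol sees risk.* Diet symptoms are a named risk and they are tested.
- *That symptoms are known to be common at baseline.* No prevalence is given.

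What the objection does not answer is why a baseline measure already collected goes unused, which visit is meant, or where a reader would find threshold crossings by arm.

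**Conclusion.** The point holds as one of efficiency, specification and reporting. The planned symptom test is valid but less precise than it could be: about 1 to 18 power points at 75 per arm under the assumed ranges, around 9 points at a latent correlation of 0.7 in the tabulated scenarios, and next to nothing at 0.3. These sizes rest wholly on assumed prevalences and correlations. That the visit is unnamed and the baseline form unused rests on the text alone.

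The absence of a by-arm event table is a secondary gap. Filling it would add transparency but almost no inferential power. Nothing here touches the primary SBP comparison, and the priority is low.

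**What to change.** In SAP section 6:

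1. State that the main symptom comparison is at 3 months, with 6 and 12 months secondary, and define in advance what rating on the form counts as a symptom being present.
2. Analyse each symptom with a binary model adjusted for the same symptom at the first screening visit, reporting the risk difference with a 95% confidence interval. Keep Fisher's test or the unadjusted comparison where events are too sparse for the model.
3. Add a table by arm, with exact confidence intervals and no tests, of serum potassium values meeting the protocol's own hyperkalemia definition, blood pressure readings meeting its own low-BP threshold (with symptoms where recorded), and serious adverse events.
4. Before counting potassium events, reconcile the hemolysis wording in Protocol section 12 and state the resulting counting rule in the SAP.

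The cost is SAP text and a few table rows. The symptom form, potassium, blood pressure and serious events are already collected. One limit: the measurement schedule lists no specific form for symptoms during blood pressure measurement, so the symptomatic part of the low-BP row depends on what staff record.
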